1.1 Clinical Experience with VeraCept

1.1.1 Pilot Study

A pilot study of VeraCept in a population of parous women demonstrated the safe use of the study drug in approximately 463 subjects total in 2 phases of the study, representing approximately 6,706 combined women-months (558 women-years) of experience.

In this time period, there were no serious adverse events (SAEs) due to the study drug or its placement. The discontinuation rate due to tolerability reasons was low. There were no intrauterine pregnancies over the course of the study, and a single SAE (an ectopic pregnancy) that was reported early in the first of 2 phases of the study.

VeraCept was successfully placed in all enrolled subjects with no peri-procedural adverse events (AEs) and without the use of anesthetics, pre-medication or mechanical dilatation. VeraCept, in this initial experience, satisfied the objectives of providing a safe, easy-to-place, conformable, low-dose copper contraceptive that is highly tolerated.

In the second confirmatory phase of the pilot study, the subject continuation rate was 90% at 10 months, with a 2% expulsion rate and a 3% discontinuation due to tolerability rate. The remaining 5% of subjects discontinued due to other reasons (e.g., the desire to get pregnant or inability to comply with study follow-up requirements.)

1.1.2 Blinded, Randomized, Comparative Study

Subsequent to the pilot study, a randomized, subject-blinded comparative study of VeraCept vs. the Optima T380S IUS was conducted in a population of parous women enrolled at a single site [9].

A total of 300 women were enrolled with 199 randomized to VeraCept and 101 to the Optima T380S control arm. Insertion was successful in 99% of all subjects. No subjects developed clinical infection or reported SAEs. Statistically significant improvements in subject continuation rates at 12 and 24 months were demonstrated with VeraCept compared to the control T380S IUS. Tolerability (pain and bleeding), study drug expulsion, and pain at insertion were also all statistically significantly improved with VeraCept versus T380S. One ectopic pregnancy was identified at the 12-month follow-up in a VeraCept user. No other pregnancies were diagnosed. With 297.3 and 132.4 woman-years, pregnancy rates were 0.3 and 0.0 per 100 woman-years for VeraCept and T380S, respectively.

1.1.3 Phase 2, Open-label, Single-Arm Study

A US Phase 2, multicenter, open-label, single-arm study (Protocol CMDOC-0008) was conducted to evaluate the effectiveness, study device placement, safety and tolerability of VeraCept at 12 months, with a 24-month extension phase to a total of 36-months study participation. The final 36-month analysis has been completed. A total of 286 subjects, parous and nulliparous premenopausal women between the ages of 18-40 years, were enrolled at 12 investigational sites in the US. VeraCept was successfully inserted in 283 subjects (99%). Placement was reported to be "easy" or "very easy" for 259/283 subjects (92%) in the safety population. At least some device placement pain was reported by 240/283 subjects (85%). Device placement pain was rated as "some pain" by 137/283 subjects (48%), "painful" by 49/283 subjects (17%), "moderately painful" by 42/283 subjects (15%), and "very painful" by 12/283 subjects (4%). Most subjects (86%) did not require mechanical dilation.

The one-year findings demonstrated that VeraCept was effective through 13 cycles of use: a single pregnancy was reported among the 250 subjects in the evaluable for pregnancy (EP) population, equating to a Pearl index of 0.52 (95% CI: 0.01, 2.87). By Kaplan-Meier analysis, the cumulative probability for remaining pregnancy free through Day 365 was 0.995.

The favorable safety, tolerability, and effectiveness data observed at one year in the Phase 2

study supported the initiation of the Phase 3 clinical trial for VeraCept.

Subjects were allowed to remain in the study, in the extension phase, for an additional 24 months and for a total of 36 months of study participation. Overall, 177/286 subjects (62%) chose to continue in the extension phase and of those, 107/177 subjects (60%) completed 36 months. The 36-month findings continue to demonstrate VeraCept's contraceptive efficacy. A second pregnancy occurred during the extension phase of the study,

with a cumulative 3-year Pearl index for all EP subjects of 0.73 (95% CI: 0.09, 2.65).

VeraCept was shown to be easily placed by Investigators and was well tolerated by subjects with a safety and tolerability profile comparable to other intrauterine copper contraceptives. During the 36-month study duration, AEs led to discontinuation for 51/283 subjects (18%) and most were reported as mild or moderate in intensity. A total of 11 SAEs were reported in 10 subjects after 36 months of VeraCept use; 8 of these were assessed as unrelated by Investigators and 3 were deemed unlikely related (hemorrhagic ovarian cyst, ectopic pregnancy, and pelvic inflammatory disease). Therefore, the 36-month data for this Phase 2 study demonstrated VeraCept to be effective, safe, and well-tolerated as a long-acting intrauterine contraceptive (CMDOC-0008 Clinical Study Report).

2 STUDY DURATION

[figure not shown]
Subject enrollment will take approximately 9 months. Each VeraCept subject will be followed for up to 8 years. Women requesting VeraCept removal for a desired pregnancy may be followed for up to one year after the IUS is removed. The total study duration for a subject being followed for return to fertility could be up to 9 years. Any on-treatment pregnancies or off-treatment pregnancies with exposure to VeraCept will be followed through delivery and for at least 6 weeks post-delivery.

3 INVESTIGATIONAL PRODUCT DESCRIPTION

3.1 VeraCept

VeraCept is designed for use as a birth control method. The study drug consists of a nitinol spring with copper sleeves at both the distal arms and proximal stem. The study drug is shaped such that upon placement in the uterus, the nitinol spring positions itself at the fundus, with the copper sleeved arms near the ostia of the fallopian tubes and copper sleeved stem at or near the internal os of the cervix. Figure 1 illustrates the basic design and layout of the study drug.

[figure not shown]
Figure 1: Schematic of VeraCept

The amount of copper utilized in VeraCept is 175 mm² exposed surface area. This compares to 380 mm² of copper surface area for the Paragard IUS. Because of its spring action, VeraCept can place concentrated amounts of copper in anatomically relevant positions within the uterus, which is designed to result in a more efficient elution profile for contraception. VeraCept is preloaded in an inserter that is used to place the sterile study drug in the uterus. VeraCept is retrieved with a standard monofilament polypropylene retrieval thread.

Figure 2 (left) shows the study drug in its pre-loaded state (directly from the package) in the distal end of the inserter. Figure 2 (right) shows a schematic of the study drug oriented in the uterus post placement.

Figure 2: Schematic of VeraCept in Pre-loaded State and Post-uterine Placement at Fundus

4 STUDY TREATMENTS

After the risks and benefits of study participation have been explained to the candidate, her questions have been answered, she has signed a written consent and assent, if applicable, and Protected Health Information (PHI) form, and eligibility has been established, a subject

identification number will be assigned by the study sponsor or designee. If the subject has a current IUS and pain is present from removal of the IUS, VeraCept insertion should not occur until the pain has resolved.

4.1 Dosage and Formulation

VeraCept contains 175 mm² of exposed copper surface area. A single VeraCept design and dosage will be used in this study. VeraCept will be supplied by Sebela. For further details, see the VeraCept Intrauterine Contraceptive Investigator's Brochure.

4.2 Supply and Administration

VeraCept is preloaded in the inserter and packaged as a single-use sterile IUS. Subjects will have VeraCept placed on "Day 1" of the trial. VeraCept should be stored in its sterile sealed package until study drug placement.

See the Investigator's Brochure for a more detailed VeraCept product description, and the VeraCept Clinician's Quick Guide for placement instructions.

4.3 Storage and Accountability

VeraCept should be stored at 25°C (77°F), with excursions permitted between -20°C to +50°C (-4°F to 122°F).

Study drug accountability, reconciliation, and record maintenance are responsibilities that must be performed by the study site in accordance with all applicable regulatory requirements. Please refer to Appendix 1 for a detailed list of Investigator Responsibilities. All unused study drug will be stored for inventory and collection. The IUS may be analyzed for residual copper to estimate the rate of release of copper. All removed/used devices should be retained until further instructions from Sebela. Cleaning, storage, and shipping instructions are detailed in the Study Reference Manual.

4.4 Dosage Modifications

All subjects will receive the same VeraCept dosage of 175mm² exposed copper surface area. No study drug will be replaced if an expulsion or removal occurs.

4.5 VeraCept Placement Confirmation

Subjects will be instructed on how to check for the presence of the IUS by feeling for the strings in the vagina. Subjects will not be required to routinely check for the study IUS presence, but if a subject believes the study IUS may have been expelled or is no longer in place, the subject can check for the string if desired. If the subject does not feel the strings, feels more than the strings or has expelled the study IUS, the subject should be instructed to immediately call for an urgent study visit and refrain from having sex or use appropriate non-hormonal contraception until further evaluation is completed. In the event that the IUS strings cannot be located during a pelvic exam string check, a transvaginal ultrasound (TVUS) should be performed to confirm IUS presence and appropriate position. All transvaginal ultrasounds should be sent to the sponsor designated central reader to confirm

the results. If the IUS has been expelled, the subject should be discontinued; a new study IUS should not be inserted. If the strings are not visible or palpable in the vaginal cavity but the TVUS confirms adequate placement in the uterus, the subject may continue. At future visits if the IUS strings are not visible then a TVUS should be repeated to re-confirm placement.

4.6 VeraCept Removal

4.6.1 VeraCept Pre-Removal Planning Timing Guidelines

Prior to VeraCept removal, the Pre-Removal Planning Timing Guidelines (Appendix 4) must be considered to prevent unintended pregnancy after removal. It is important that VeraCept removal and the initiation of the next method of contraception occurs as per the pre-removal timing guidelines. If the subject is unable to or unwilling to comply with the pre-removal timing guidelines, it should be determined if the subject has had vaginal intercourse within 7 days prior to removal. If intercourse within 7 days prior to removal is confirmed, VeraCept removal and the Exit Visit should be rescheduled. If rescheduling is not possible, emergency contraception (EC) should be provided at time of removal if vaginal intercourse occurred within the EC effectiveness window. All subjects must be instructed to continue use of new contraception method for 14 days after removal. Subjects must be educated on the risks of pregnancy if the recommended pre-removal timing guidelines are not followed.

4.6.2 VeraCept Removal Procedure

Ensure all items needed for VeraCept removal are readily available, including additional tools that may be required for a difficult removal or a removal without visible threads (see Appendix 5).

Instructions for VeraCept removal are detailed in Appendix 5.

All removed/used devices should be retained until further instructions from Sebela. Cleaning, storage, and shipping instructions are detailed in the Study Reference Manual.

5 OBJECTIVES AND ENDPOINTS

5.1 Objectives

The primary objective of the study is to assess the contraceptive efficacy (prevention of pregnancy) of VeraCept.

The secondary objectives of the study are to assess the following for VeraCept:

- Safety and tolerability
- Return to fertility after VeraCept removal, only for subjects requesting VeraCept removal to become pregnant

5.2 Endpoints

Primary Endpoint

The primary endpoint is the contraceptive efficacy through 3 years of use, as assessed by the Pearl Index. The Pearl Index will be calculated for Years 1, 2 and 3 as well as cumulatively through Year 3.

Secondary Endpoints

Secondary endpoints include:

Contraceptive Efficacy

- Pearl Index at Years 4, 5, 6, 7 and 8 as well as cumulatively through Years 4, 5, 6, 7 and 8.
- Pregnancy percentage by life table analysis (Kaplan Meier) at Years 1, 2, 3, 4, 5, 6, 7 and 8.
- Separate analyses will be performed only for the last 3 years of the study (Years 6-8) using the EP population. The cumulative Pearl Index for Years 6 to 8 will be calculated as well as the cumulative pregnancy percentage for Years 6 to 8 using a life table analysis (Kaplan-Meier).

Study Drug Placement

- Ease of VeraCept placement
- Placement success

Safety

- Serious adverse events (SAEs)
- Adverse events (AEs)
- Pelvic infection (pelvic inflammatory disease (PID) or endometritis)
- Ectopic pregnancies
- Uterine perforations
- Dysmenorrhea
- Abdominal pain
- Expulsion rates at Years 1, 2, 3, 4, 5, 6, 7 and 8

Tolerability

- Bleeding and spotting patterns
- Insertion pain assessed immediately after insertion
- Continuation rates at Years 1, 2, 3, 4, 5, 6, 7 and 8

Reasons for discontinuation

Return to Fertility

• Pregnancy rate in subjects who request VeraCept removal specifically to become pregnant. Subjects who desire pregnancy after having VeraCept removed will be followed for either 1 year, until they decide to no longer try to conceive or they become pregnant, whichever comes first.

The primary and secondary endpoints for the study will be reviewed after at least 200 subjects have completed 3 years of treatment to assess if the data supports the filing of an NDA for approval of an indication with 3 years of use. The data up to 8 years of treatment will be continually assessed to determine if the data supports additional NDA filings in order to extend the use of VeraCept beyond the initial planned 3 years of use.

6 BENEFITS AND RISKS

6.1 Potential Benefits

No assurances or guarantees can be made regarding the benefits of VeraCept to the study subject. The potential benefits of VeraCept include that it is a hormone-free contraceptive method that requires only professional placement to be effective.

6.2 Potential Risks/Adverse Reactions

Evidence from prior clinical studies has demonstrated that the use of VeraCept has low rates of SAEs or AEs, and that pregnancy failure rates (intrauterine and ectopic pregnancy) have been low.

The following AEs have been reported in $\geq 2\%$ of pooled subjects in the three VeraCept studies (CMDOC-0008, CMDOC-0042, and CMDOC-0045) through 3 years of use. AEs designated with an asterisk (*) indicates AEs that were considered at least possibly related to VeraCept and/or the VeraCept placement/removal procedure in $\geq 2\%$ of pooled subjects. This list is in alphabetical order and not in order of increasing/decreasing occurrence:

- Abdominal distension
- Abdominal pain lower
- Abdominal pain upper
- Abdominal pain*
- Acne
- Anxiety
- Arthralgia
- Back pain*
- Bacterial vaginosis*
- Coital Bleeding*
- COVID-19
- Depression

- Device expulsion*
- Diarrhea
- Dizziness
- Dysmenorrhea*
- Dyspareunia*
- Fatigue
- Headache
- Heavy menstrual bleeding*
- Influenza
- Insomnia
- Intermenstrual bleeding*
- Ligament sprain
- Menometrorrhagia*
- Migraine
- Nasopharyngitis
- Nausea
- Oropharyngeal pain
- Ovarian cyst
- Pelvic discomfort*
- Pelvic pain*
- Pharyngitis streptococcal
- Post procedural discomfort*
- Post procedural hemorrhage*
- Procedural pain*
- Sinusitis
- Upper respiratory tract infection
- Urinary tract infection
- Vaccination complication
- Vaginal discharge*
- Vomiting
- Vulvovaginal mycotic infection

In addition, the following clinically significant adverse events have been reported in <2% of pooled subjects in the VeraCept studies:

- Uterine hemorrhage
- Anemia as a result of uterine hemorrhage, which may lead to the need for blood transfusion
- Ectopic pregnancy
- Ruptured ectopic pregnancy
- Increased risk of spontaneous abortion if pregnancy occurs with VeraCept in place. Remove VeraCept if pregnancy occurs.

- Pelvic infection (pelvic inflammatory disease, endometritis), which can lead to fallopian tubal damage leading to ectopic pregnancy or infertility, hysterectomy, sepsis and rarely death
- Uterine perforation, which may require laparoscopy or laparotomy to remove VeraCept from the peritoneal cavity
- Embedment, which may require additional in clinic procedures or surgical removal

There may also be risks that are unanticipated at this time. See the VeraCept Investigator's Brochure for a complete list of reported adverse events and additional information.

Although pregnancy is not considered an adverse event, there is a possible risk of becoming pregnant while using VeraCept.

In addition to the above known risks, the following additional adverse events have been reported in association with Paragard T380A IUS(16). Adverse events associated with the Paragard T380A IUS may be relevant because it is also a copper-based contraceptive. The severity or frequency of any of the following events, should they occur, is not expected to be any different with the use of VeraCept. These events are not in order of severity or frequency.

- Risks with Intrauterine Pregnancy: septic abortion, premature delivery, sepsis, septic shock and death if pregnancy occurs.
- Sepsis: Group A streptococcal infection has been reported; strict aseptic technique is essential during insertion

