18 ON-TREATMENT PREGNANCY DETERMINATION AND FOLLOW UP

Confirmed or suspected pregnancies are required to be immediately reported to Sebela. Ontreatment suspected pregnancy will be confirmed with both a urine and serum pregnancy test. Pregnancies will be promptly confirmed and dated by ultrasound evaluation and medical assessment as needed. Presence or absence of the study drug will also be determined by ultrasound. Removal of the study drug, if in place, will be performed as deemed appropriate by the study physician and upon obtaining subject consent/assent (note: removal itself may be performed by another clinician, such as a nurse practitioner). Consideration of study drug removal should include the following standard of care criteria: If the subject has an intrauterine pregnancy in the first trimester and the study drug is seen to be in the uterine cavity or cervix on ultrasound, remove the study drug if the retrieval threads are visible. If the retrieval threads are not accessible, the IUS should remain in the uterus until delivery (abortion or term).

Subjects will be counseled and followed for at least 6-weeks post-delivery, and the clinical outcome will be recorded. Any infant abnormalities should be reported.

See Pregnancy Reporting Guidelines in Study Reference Manual (Appendix 7) for additional instructions.

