4.12.8 Cumulative VeraCept Continuation Rates

Cumulative VeraCept continuation rates for Years 1 through 5 will be estimated via Kaplan-Meier method for the Safety population. The complementary log-log transformation will be used to construct 95% CIs. The number and percentage of subjects with each reason for discontinuation will be summarized. The analysis will also by repeated by parity at enrollment.

Time to VeraCept discontinuation from successful insertion will be analysis variable.

- If a subject discontinued VeraCept because of desire of pregnancy, the subject will be censored at the cycle of removal.
- If a subject discontinued because of pregnancy, VeraCept should be removed. However, according to protocol, the study drug could be removed at the time of delivery. So, for consistency, the subject will be censored at the cycle of removal or conception if not removed.
- If a subject is lost to follow-up, she will be censored at the last cycle in which the study drug was known to be in place.
- If a subject completed the exposure period, the subject will also be censored at the cycle of the period end.

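### Protocol 6.2 says to remove VeraCept whenever pregnancy occurs, Section 18 says to leave it in place when the threads are not accessible, and no text says which governs

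*Protocol*

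**What the plan says.** Protocol Section 6.2 lists clinically significant events seen in fewer than 2% of pooled subjects. One bullet begins "Increased risk of spontaneous abortion if pregnancy occurs with VeraCept in place" and ends with an instruction: "Remove VeraCept if pregnancy occurs". The instruction sets no limit by trimester, site of pregnancy, thread visibility or consent, and does not refer to Section 18.

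Protocol Section 18 is the section on on-treatment pregnancy. Its general rule is "Removal of the study drug, if in place, will be performed as deemed appropriate by the study physician and upon obtaining subject consent/assent". It then gives criteria to consider. For a first-trimester intrauterine pregnancy with the device seen in the cavity or cervix, the direction is "remove the study drug if the retrieval threads are visible". The next sentence is "If the retrieval threads are not accessible, the IUS should remain in the uterus until delivery (abortion or term".

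Protocol Appendix 5 gives removal instructions, including a route for removal when no threads are visible. The text shown makes no exception for a pregnant subject.

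SAP 4.12.8, on continuation rates, says "If a subject discontinued because of pregnancy, VeraCept should be removed", then "However, according to protocol, the study drug could be removed at the time of delivery", and concludes that "the subject will be censored at the cycle of removal or conception if not removed".

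**The concern.** A site that finds a pregnancy with the device in the uterus and no reachable threads has one section telling it to remove and another telling it to leave the device until the pregnancy ends. Section 6.2 is a risk list, but the sentence is an order, not a description of a risk. The revision history records updates to the potential risk section in both version 6.0 and version 7.0. A site could therefore take 6.2 as the more recent text, although the log does not show when this sentence was added. Appendix 5 then offers a way to act on it, because its route without visible threads extends to passing an instrument into the uterine cavity, cervical dilation and hysteroscopy.

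The stake is patient safety. Section 6.2 names spontaneous abortion as a risk of pregnancy with VeraCept in place. For a marketed copper IUS it adds septic abortion, premature delivery, sepsis and death. Section 18 also requires pregnancy outcomes to be followed and recorded, and outcomes would be harder to interpret if sites managed these pregnancies differently. Follow-up runs to Year 8, so such pregnancies can still occur.

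**Working it through.** No figure in the plan depends on this sentence, so the main check compares the texts case by case.

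| Case (device in place) | Section 6.2 | Section 18 | Result |
|---|---|---|---|
| First-trimester intrauterine pregnancy, threads visible | Remove | Remove | Agree |
| Threads not accessible | Remove | Leave until the pregnancy ends | Direct conflict |
| Physician does not judge removal appropriate, or subject does not agree | Remove, no condition | Conditional on both | Differ in strength |
| Later pregnancy with visible threads, or ectopic pregnancy | Remove | General rule only | 6.2 is the only explicit instruction |

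Section 18 also uses two terms. Removal is tied to threads that are visible, and retention to threads that are not accessible. Threads that are out of sight but within reach are not clearly covered by either.

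**Precedence.** Neither section ranks itself against the other, and neither cross-refers. Appendix 5 points to neither on pregnancy.

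**Effect on the primary analysis.** SAP 4.1.5 gives a pregnancy before removal the study day of conception, and SAP 4.1.6 counts it as an on-treatment pregnancy. Whether the device is later removed or left changes neither the count nor the event date, so the Pearl Index numerator is unaffected.

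**Effect on continuation.** Under SAP 4.12.8 the censoring cycle is that of removal if the device is removed, and of conception if it is not. The cycle can therefore depend on which protocol section a site followed. This is the only statistical consequence found.

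**Can the affected pregnancies be counted?** The nearest attempt is as follows.

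- Inputs: 1,480 women up to age 35, 620 of them with at least 3 years of use, and 577 evaluable woman-years in Year 3 (Protocol 20.9). The Phase 2 three-year Pearl Index is 0.73, 95% CI 0.09 to 2.65 (Protocol 1.1.3).
- Assumption: constant yearly retention, (620/1,480)^(1/3) = 0.748.
- Evaluable woman-years: Year 2 = 577/0.748 = 771; Year 1 = 771/0.748 = 1,031; total = 1,031 + 771 + 577 = 2,379.
- Expected on-treatment pregnancies through Year 3: 2,379 × 0.73/100 = 17.4. Over the Phase 2 interval: 2,379 × 0.09/100 = 2.1 to 2,379 × 2.65/100 = 63.0.

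This counts every on-treatment pregnancy in the EP population. It includes conceptions up to 7 days after removal or expulsion, when no device is in place, as well as pregnancies with visible threads. It leaves out women aged 36 to 45 and Years 4 to 8. The share with the device in place and threads not accessible is needed to go further, and the documents do not give it.

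**The case against.** The strongest reply is that Section 18 plainly governs. It is the specific section on managing an on-treatment pregnancy, while the 6.2 sentence is the tail of one bullet in a risk list. A site facing a pregnancy would turn to Section 18, which requires immediate reporting to the sponsor and points to further guidance in the Study Reference Manual, not available here. Section 6.4 adds ongoing evaluation of pregnancies by the medical monitor and a monthly review. This makes divergent management less likely, and nothing in the documents shows that it has occurred. It does not remove the conflict, because no text gives Section 18 precedence and 6.2 is worded as an instruction.

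A reader might also infer more than the documents support:

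- **That every pregnancy with the device in place gets opposite instructions.** The sections agree for a first-trimester intrauterine pregnancy with visible threads.
- **That Section 18 directs retention in all other cases.** It does so only when threads are not accessible; elsewhere it relies on judgement and agreement.
- **That about 17 pregnancies are affected.** That figure counts a different and wider group.
- **That the primary endpoint is at risk.** The numerator does not depend on removal.
- **That the SAP is a third conflicting instruction to sites.** SAP 4.12.8 is a censoring rule, and it already provides for both outcomes.

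**Conclusion.** The point holds in a narrow form. Protocol 6.2 and Section 18 contradict each other for an on-treatment pregnancy with the device in place and threads not accessible. They also differ in strength wherever Section 18 makes removal conditional. This is an internal inconsistency in clinical management and matters for patient safety. The number of affected pregnancies cannot be sized from the documents. There is no effect on the Pearl Index numerator, and the statistical reach is limited to a censoring cycle in the continuation analysis.

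The conclusion rests on the text available. The Study Reference Manual was not seen and may contain a ruling. The statement about Appendix 5 applies only to the part shown. Which instruction is clinically right is not judged here.

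**What to change.** The sponsor's clinical team should reconcile Protocol 6.2 and Section 18 into one instruction, with Section 6.2 referring to Section 18. While doing so it should settle the cases where only 6.2 speaks explicitly, and the difference between visible and accessible threads. Appendix 5 should be checked for consistency with the result, and sites should be notified. SAP 4.12.8 needs at most its opening sentence aligned with the reconciled wording; its censoring rule can stand.

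The cost is a wording change in the protocol and a notice to sites. Sample size, data collection and the planned analyses do not change.
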